
4. To evaluate the safety of different investigational therapeutics as compared to the control arm as assessed by:
 
 • Cumulative incidence of SAEs through Day 29. • Cumulative incidence of Grade 3 and 4 clinical and/or laboratory AEs through Day 29. • Discontinuation or temporary suspension of study product administrations (for any reason) • Changes in complete blood count with differential, hemoglobin, platelets, creatinine, glucose, total bilirubin, alanine aminotransferase (ALT), aspartate aminotransferase (AST), and prothrombin time (PT) reported as international normalized ratio (INR) over time (analysis of lab values in addition to AEs noted above). 	
 • SAEs • Grade 3 and 4 AEs • Change in total WBC number, neutrophil number, lymphocyte number, hemoglobin, platelets, creatinine, glucose, total bilirubin, ALT, AST, and PT/INR from Day 1 to Days 2, 4, and 7 (while hospitalized); and Days 15 and 29 (if attends in-person visit or still hospitalized).
Exploratory	

1. To examine if the effect of convalescent plasma is associated with the days of symptoms at time of plasma administration
	
 • Plasma administered on day ≤ 7 vs. >7 days of symptoms on primary outcome

2. To examine if effect of convalescent plasma differs by comorbidities
	
 • Primary outcome in persons with ≤ 2 or ≥ 3 comorbidities (age ≥ 65 years, chronic lung, cardiac and renal disease, hypertension, diabetes, obesity and immunosuppression)

3. Research sample collection and management for future investigations:
 
Respiratory samples on days 1, 4, 7, 15, 29 and 30 mL of blood on days 1, 2, 4, 7 in hospital and days 15 and 29 in- or outpatient.
	
 • Sample Collection (Research lab draw with routine labs), preparation, labeling, shipping, storage and monitoring will be addressed in a future amendment.

4. Impact of donor convalescent plasma parameters on the activity of administered plasma
	
 • Donor plasma samples retained by Vitalant Blood services and provided to CURES-1 investigators will be tested for antibody levels, neutralization against SARS-CoV2, inflammatory and other mediators in relation to clinical and laboratory outcomes in study subjects.

World Health Organization (WHO) Ordinal Scale

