8.2 BASELINE, RANDOMIZATION AND PRODUCT ADMINISTRATION

Baseline assessments should be performed before the first study product administration.

The following eligibility/baseline assessments can be done up to 72 hours prior to randomization time: demographic information (age, ethnicity, gender, body mass index), medical history/baseline comorbidities (e.g. obesity, smoking, diabetes, hypertension, cardiac, renal, liver, and lung disease), and physical exam.

Baseline clinical status data are collected right before randomization. Baseline vital signs (NEWS2) should be collected closest to randomization time and must be collected within 24 hours prior to randomization time.

The following additional baseline assessments are collected prior to study product administration:

- COVID-19 signs and symptoms, including day of onset,
- Medications for this current illness taken in the 7 days prior to Day 1 (See Section 6.5),
- Designated pre-admission medications by class (See Section 6.5),
- Adverse events (See Section 8.5),
- Safety and research labs (See Section 8.4).

Day 1 safety and research labs should be collected up to 24 hours prior to randomization and before first study product administration. Laboratory tests performed as part of routine clinical care within the same time period will be accepted for Day 1 safety laboratory tests.

Ideally, product administration should start on the same day as randomization (Day 1), but may be started up to 36 hours after randomization.

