2.4.7 SUB-GROUP ANALYSES

Subgroup analyses for the primary outcome will evaluate the treatment effect across the following subgroups:

- 1) Received study product (plasma/saline) ≤ 7 days vs. >7 days after onset of symptoms
- 2) Have ≤ 2 vs. ≥ 3 comorbidities at baseline (age ≥ 65 years, underlying chronic lung, heart, kidney disease, hypertension, diabetes, obesity or immunosuppression)
- 3) Age <65 vs. ≥ 65
- 4) BMI <35 vs. ≥ 35

A forest plot will display point estimates and confidence intervals across subgroups. Interaction tests will be conducted to determine whether the treatment effect varies by subgroup. We may adjust for selected baseline covariates in the assessment of interactions. We anticipate that convalescent plasma has a larger benefit in those treated early (≤ 7 days after onset of symptoms), having more comorbidities at baseline, or older (≥ 65 years old), and a smaller benefit in obese individuals.

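### Effect modification by symptom days, comorbidity count, age and BMI is tested only on two-level cuts; pre-specifying continuous interaction tests alongside them would be a cheap improvement

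*Combined protocol and SAP*

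**What the plan says.** Table 2 (Section 3, Exploratory 1) states the objective as "To examine if the effect of convalescent plasma is associated with the days of symptoms at time of plasma administration" and gives the endpoint as "Plasma administered on day ≤ 7 vs. >7 days of symptoms on primary outcome". Exploratory 2 does the same for comorbidity: "Primary outcome in persons with ≤ 2 or ≥ 3 comorbidities". Section 8.3.5 repeats both splits.

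Section 9.4.7 (printed 2.4.7) lists four subgroup factors, each at two levels: "Received study product (plasma/saline) ≤ 7 days vs. >7 days after onset of symptoms"; "Have ≤ 2 vs. ≥ 3 comorbidities at baseline"; age below 65 or not; BMI below 35 or not. It plans a forest plot and says "Interaction tests will be conducted to determine whether the treatment effect varies by subgroup". It names no continuous, trend or spline interaction. It also states expected directions: "We anticipate that convalescent plasma has a larger benefit in those treated early", with further expectations for more comorbidities, older age and obesity.

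Section 8.2 collects the underlying values: "COVID-19 signs and symptoms, including day of onset", together with age, body mass index and individual comorbid conditions. Section 6.1.2 has the start time of each transfusion recorded. Days from onset to study product can therefore be computed. Section 9.4.1 says that a statistical analysis plan will be written before unblinding and database lock.

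**The concern.** The timing objective is worded as a question about a quantity, and the endpoint answers it with two groups. The split treats a patient infused on day 1 like one infused on day 7, and puts days 7 and 8 on opposite sides. The documents do not justify day 7 as a change point. The only timing figure in the benefit section (2.3.2) is four days, and that is for influenza.

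Early treatment is central to the rationale in Section 4.2. The trial is sized for the overall effect, so any interaction test starts with limited power. If the effect fades gradually with time since onset, or changes at a day well away from 7, the planned test gives up part of that power even though the day-level data are in hand. What is at stake is the chance of detecting a timing effect, and to a lesser degree one by comorbidity count, age or BMI.

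**Working it through.** **1. The plan's own figure.** Section 9.2: 30% vs 20%, two-sided 0.05, 85% power, 1:1. With the unpooled z-test, n per arm = (1.960 + 1.036)² × (0.30×0.70 + 0.20×0.80) / 0.10² = 8.978 × 0.37 / 0.01 = 332.2, so 333 per arm and 666 in total, as in Table 6. 666/0.95 = 701.05, consistent with 702 randomized. The planned effect is an odds ratio of (0.20/0.80)/(0.30/0.70) = 0.58. The documents state no power for any interaction test.

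**2. Information kept by a cut.** For an interaction that is linear in the modifier X, the loss is L = 1 − corr(X, cut X)². The documents give no mean, SD or share on either side of a cut, so every distribution below is an assumption.

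- Normal, cut at its median: L = 1 − 2/π = 36.3%.
- Days uniform on 1 to 14, cut at 7: variance (14² − 1)/12 = 16.25; group means 4 and 11; between-group variance 0.25 × 7² = 12.25; L = 1 − 12.25/16.25 = 24.6%.
- Days gamma, normal or lognormal, SD 3-5: about 33-46% for means of 5-8 days and 39-63% for means of 9-10.
- Comorbidity count of 0-8 cut between 2 and 3: about 28-43% for means 1.5-3 and 35-56% for means 3.5-4.

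The overall range is about 25-63%. No calculation was made for age or BMI.

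**3. What a loss does to power.** Take a test with 80% power on the full value (1.960 + 0.842 = 2.802). With L = 36.3% its power on the cut is Φ(2.802 × √0.637 − 1.960) = Φ(0.276) = 61%. Recovering that would need 1/0.637 = 1.57 times the participants.

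**4. Simulation.** 666 participants, 1:1, 30% control risk, gamma symptom days (mean 6-8, SD 3-4), a logistic model with treatment, modifier and their product, and a two-sided 5% Wald test. Ranges run over the assumed distributions. The steep gradient has a log-odds slope of ln(1.2/0.25)/13 = 0.121 per day, and the moderate one ln(0.80/0.40)/13 = 0.053.

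| Assumed true effect (OR, plasma vs saline) | Power, days continuous | Power, ≤7 / >7 split |
|---|---|---|
| Steep gradient: 0.25 at day 1 to 1.2 at day 14 | 53-78% | 37-59% |
| Moderate gradient: 0.40 to 0.80 | 13-22% | 10-17% |
| Step at day 4 (0.35 to 1.0) | 22-43% | 16-23% |
| Step at day 10 (0.35 to 1.0) | 24-53% | 16-32% |
| Step at day 7 (0.35 to 1.0) | 56-60% | 76-83% |
| Ramp over days 5-9 (0.4 to 1.0) | 41-45% | 44-53% |
| Ramp over days 3-10 | 32-38% | 32-37% |

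Both tests have a type I error of about 5%. With 1,500 runs per setting the Monte Carlo standard error is at most √(0.25/1500) = 1.3 points, and repeat runs moved the ranges by a few points without changing the ordering. The gap in favor of days is about 14-22 points for the steep gradient and 2-7 points for the moderate one.

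**The case against.** Four arguments favor leaving the plan alone.

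- **The cuts match the stated expectations.** A reader might infer that the protocol's hypotheses are all gradients and that the tests contradict them. The sentence in Section 9.4.7 goes on to define early as within 7 days of onset and older as at least 65, and it refers to obese individuals as a group. Only the comorbidity expectation reads as a gradient. Age 65 is also a randomization stratum (Section 6.3.1). This stands: the mismatch is with the wording of Exploratory objective 1, not with Section 9.4.7.
- **A linear term is itself an assumption about shape.** It loses to the split for a step at day 7, and ties or loses for a ramp over days 5-9. This stands, so a reader should not conclude that the split brings no benefit, or that it wins only for a step exactly at the cut.
- **With moderate gradients neither test does well.** An odds ratio running from 0.25 to 1.2 implies harm in late patients and is extreme beside a planned overall odds ratio of 0.58. At 0.40 to 0.80 the coding would seldom change the conclusion. This stands and limits the size of the gain.
- **The analyses are exploratory and a SAP is still to come.** True, but nothing in the text commits that SAP to a continuous interaction.

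A reader might also infer that a non-significant split would be reported as showing that timing does not matter. The documents say nothing of the kind.

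**Conclusion.** The point holds as a cheap improvement. All four modifiers are tested only on two-level cuts of collected values, and for symptom days this sits poorly with the objective as worded. Under a roughly smooth effect, or a step well away from day 7, the split is less likely to detect effect modification: by about 14-22 points of power for a steep gradient and 2-7 points for a moderate one.

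These sizes rest on assumed gamma symptom days, 666 participants and a 30% control risk. A single narrow loss, such as a figure in the mid-thirties of percent, is tempting to state as fact. The documents cannot support it, because they give no distribution; about 25-63% is the defensible range. No figure supports a claim about age or BMI. The comorbidity count already contains two cut values (age at least 65, and obesity), so using the full count recovers only part of the detail there.

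The primary and key secondary results are unaffected.

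**What to change.** In Section 9.4.7, and in the SAP to be written before unblinding, pre-specify a treatment-by-continuous-value interaction in the logistic model. Do this first for days from symptom onset to start of study product, and also for comorbidity count, age and BMI. Add a restricted cubic spline as a check on shape. Keep the existing cuts for the forest plot and the subgroup estimates, and report both interaction tests for each modifier. The endpoint column of Table 2 for Exploratory 1 and 2 can then point to both.

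Cost: a few lines of text and four model terms, with no new data, participants or procedures. Placed in the SAP alone it is SAP wording; editing Section 9.4.7 or Table 2 is a protocol amendment and needs VA CIRB approval under the Statement of Compliance. There is one additional exploratory test per modifier, so the reporting should say that these tests are exploratory. The linear term has less power than the split if the true effect changes abruptly at or close around the cut, which is the reason to keep and report both.

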4 STUDY DESIGN

4.1 OVERALL DESIGN

The VA CoronavirUs Research and Efficacy Study-1 (VA CURES-1) is designed to determine the safety and efficacy of convalescent plasma to prevent progression to respiratory failure and death among persons hospitalized with SARS-CoV-2 and who require supplemental oxygen.

This adaptive design clinical trial may involve multiple stages each investigating different interventions.

The first stage in the clinical trial is:

Stage 1: Convalescent Plasma vs Saline

If convalescent plasma is shown to be beneficial in Stage 1, we will proceed to Stage 2:

Stage 2: Convalescent Plasma vs Fresh Frozen Plasma

4.2 SCIENTIFIC RATIONALE FOR STUDY DESIGN

Convalescent plasma contains SARS-CoV-2-specific antibodies that support neutralization and other antiviral activities that will inhibit viral replication and lyse infected cells to limit underlying tissue damage and inflammation. Administration of convalescent plasma early in the course of infection in the hospital will increase the days to and prevent respiratory failure and death before irreversible lung and vascular damage ensues.

4.3 JUSTIFICATION FOR DOSE

The planned plasma volume for this study is 400-600 mL. Plasma is collected in ~200-250 mL units. All studies to date using convalescent plasma have used 200-600 mL (1-2 units) of plasma. This dose typically provides sufficient antibodies to maintain or increase virus-specific levels in plasma of recipients and is generally well-tolerated for volume. If 400-600 mL volume is deemed excessive due to e.g., congestive heart failure or oliguria, then 200-250 mL will be given if deemed safe by the primary clinicians and study staff.

4.4 END OF STUDY DEFINITION

The study is completed for each subject on day 29 (+3 days) after administration of convalescent plasma or on the day of death.

5 STUDY POPULATION

5.1 INCLUSION CRITERIA

Veterans must meet ALL of the following criteria to be eligible to participate:

1. Admitted to a participating VA clinical site with symptoms suggestive of SARS-CoV-2 infection.
2. Participant (or legally authorized representative) provides informed consent prior to initiation of any study procedures.
3. Participant (or legally authorized representative) understands and agrees to comply with planned study procedures.
4. Veteran \geq 18 years of age at time of screening.
5. Has laboratory-confirmed SARS-CoV-2 infection as determined by polymerase chain reaction (PCR) or antigen test, as documented by either of the following:
 - (1) RT-PCR or antigen positive (nasopharyngeal, oropharyngeal, saliva, lower respiratory) in sample collected \leq 72 hours prior to screening;
 - (2) RT-PCR or antigen positive in sample collected $>$ 72 hours but \leq 168 hours (i.e. 7 days) prior to screening, documented inability to obtain a repeat sample (e.g. due to lack of testing supplies, limited testing capacity, results taking $>$ 24 hours, etc.), AND progressive disease suggestive of ongoing SARS-CoV-2 infection.
6. Requiring oxygen by nasal cannula or by face-mask as a new treatment (or if previously on home oxygen, at a liter flow at least 2 Lpm greater than home prescription), but not on humidified heated high-flow nasal cannula (HHHFNC) at \geq 15 Lpm.
7. Can be randomized within 72 hours of initial hospital admission.
8. Agrees not to participate in another therapeutic clinical trial for the treatment of COVID-19 or SARS-CoV-2 through Day 29 without approval from the investigator(s). Taking part in other research studies, including those unrelated to SARS-CoV-2, without first discussing it with the investigators of this study may invalidate the results of this study, as well as that of the other study.

5.2 EXCLUSION CRITERIA

An individual who meets any of the following criteria will be excluded from participation in this study:

1. Respiratory failure requiring mechanical ventilation, non-invasive ventilation including CPAP (for an indication other than previously diagnosed sleep apnea and maintained on outpatient settings), or extra-corporeal membrane oxygenation or anticipated to require any of those treatments or to die within 24 hours.
2. Anticipated discharge from the hospital or transfer to another hospital that is not a study site within 72 hours.
3. History of previous transfusion reaction.
4. Previously documented serum IgA deficiency (<7 mg/dL)
5. Documented to have received convalescent plasma in the last 60 days.

5.3 LIFESTYLE CONSIDERATIONS

During this study, participants are asked to:

- Avoid participating in another interventional clinical trial for the treatment of SARS-CoV-2 or SARS-CoV-2. Co-enrollment for natural history studies of SARS-CoV-2 is permitted or studies unrelated to of SARS-CoV-2 can be considered if PI of both studies agree.

5.4 SCREEN FAILURES.

Following Consent and after screening evaluations have been completed, the LSI or designee will review the inclusion/exclusion criteria and determine the subject's eligibility for the study. If there is any uncertainty, the Local Site Investigator (LSI) should make the decision on whether a potential subject is eligible for study enrollment.

5.5 STRATEGIES FOR RECRUITMENT AND RETENTION

Patients recruited to the study will be from those admitted to acute inpatient medical services. Research staff will employ several strategies to identify potentially eligible subjects. No external recruitment methods are anticipated.

Materials summarizing the purpose and design of the study, key interventions, and key inclusion and exclusion criteria will be made available to clinical providers caring for patients hospitalized with SARS-CoV-2.

Potential participants will be identified by IRB-approved review of CPRS charts and hospital admission logs under a HIPAA waiver. Pre-screening for preliminary eligibility will be performed by a member of the site research team, usually the Site Coordinator, who will complete a checklist of key inclusion and exclusion criteria. If *a priori* requirements for enrollment are met, permission will be obtained, if not previously granted, from the patient's clinical provider to seek informed consent for participation in the study from the patient or his/her authorized healthcare proxy.

Over 30 VA Medical Centers have expressed interest in participating in this study. In the last three months of the epidemic, 1,890 patients with SARS-CoV-2 were admitted to the top 25 VA

medical center targeted for inclusion in this study. The study is proposed to require approximately 702 participants admitted with SARS-CoV-2, assuming a 30% primary event frequency in the study sample, to have 85% power for detecting a 10% absolute reduction in the primary event with convalescent plasma (i.e., hazard ratio 0.7). Among 568 patients admitted with SARS-CoV-2 to the Detroit VA, 69% achieved the primary endpoint of respiratory failure or death, although these frequencies may decrease with less ill patients admitted and more skilled management over time. Proactive and consistent team management and communication will be required for effective ongoing recruitment.

6 STUDY INTERVENTION

6.1 STUDY INTERVENTION(S) ADMINISTRATION

6.1.1 STUDY INTERVENTION DESCRIPTION

Patients will be randomized within 72 hours of admission to receive 1) 400-600 mL of ABO compatible convalescent plasma from the hospital blood bank or 2) sterile saline, each wrapped in non-disclosing paper with translucent tubing over approximately 4 hours. If volume overload is a concern, 200-300 mL will be infused by pump over 2 hours.

6.1.2 DOSING AND ADMINISTRATION

The dose of convalescent plasma, or placebo, that will be utilized in this study is consistent with the April 8, 2020 published by the FDA (<https://www.fda.gov/vaccines-blood-biologics/investigational-new-drug-ind-or-device-exemption-ide-process-cber/recommendations-investigational-covid-19-convalescent-plasma>). We will utilize a target dose of two units of plasma with antibodies to SARS-CoV-2, based on previously studied dosing established in SARS1, in which a weight-based dose of 5 mL/kg has been utilized.

Study intervention will be started within 36 hours of randomization, at a rate of 150 mL per hour or less. The administration of each unit should last approximately up to 2 hours, and the elapsed time between each transfusion should not exceed 12 hours. Time at start and end of transfusion should be recorded. Vital signs will be measured prior to transfusion, 10-20 minutes after start of transfusion, at completion of transfusion or if discontinued and 30-60 minutes after the end of the transfusion.

6.2 PREPARATION/HANDLING/STORAGE/ACCOUNTABILITY

6.2.1 ACQUISITION AND ACCOUNTABILITY

Convalescent plasma is obtained from contracted blood service providers, either locally or shipped overnight to requesting centers. Plasma is obtained from veterans and others who have no symptoms for 28 days after recovery from SARS-CoV-2 infection or who have no symptoms for 14-27 days and have a negative nasopharyngeal swab for SARS-CoV-2 RNA. Plasma units are stored in designated areas in the local VA Blood Bank.

Detailed information about drug handling procedures can be found in the Drug Treatment & Handling Procedures (DTHP).

6.2.2 FORMULATION, APPEARANCE, PACKAGING, AND LABELING

Blinded study intervention will be supplied to the research staff in a manner that does not identify the active versus placebo. The research staff will remain blinded to the treatment group assignment. Detailed information about drug handling procedures can be found in the Drug Treatment & Handling Procedures (DTHP).

6.2.3 PRODUCT STORAGE AND STABILITY

Clinical supplies must be stored in a secure, limited-access location under the storage conditions specified on the label. Sites are responsible for providing secure storage for study drugs in the Pharmacy or elsewhere as directed by federal and local laws, regulations, policies, and procedures. Investigational drugs must be stored separately from non-study drug inventory to avoid co-mingling of investigational and clinical drug products. Site pharmacists should consult VHA Handbook 1108.04 "Investigational Drugs and Supplies" Clinical supplies may not be used for any purpose other than that stated in the protocol. The investigational drug will be dispensed and administered only for the purposes specified in this protocol. The local site investigator (LSI) is responsible for assuring that the investigational product is administered only to study patients by qualified and approved personnel. The LSI is ultimately responsible for all study drug at their clinical site. Receipt and dispensing of trial medication must be recorded by an authorized person at the trial site.

The study product is a commercially available product with expiration dating assigned by the provider. The site will monitor the dating of all study drug to ensure that the drug will not expire through the anticipated administration and use by the patient.

Detailed information about proper storage procedures can be found in the Drug Treatment & Handling Procedures (DTHP).

